NCT01731678

April 29, 2012

Transcranial Magnetic Stimulation for Adolescent Depression (TMSAD)

INTRODUCTION

Treatment options for major depressive disorder (MDD) in youth are limited, with concerns over efficacy (Carvalho et al., 2007) and safety (Adegbite-Adeniyi et al., 2012; Menke et al., 2012; Cipriani et al., 2016). Evidence suggests 30-50% of adolescents and young adults with MDD are treatment-resistant, leading to lifelong consequences (Fava, 2003). Consequently, new interventions for treatment-resistant MDD in youth are needed (Souery et al., 2011). One potential treatment is repetitive transcranial magnetic stimulation (rTMS)(MacMaster et al., 2016). Prior research demonstrates that rTMS targeting the left dorsolateral prefrontal cortex (DLPFC) in adults is well-tolerated, safe, and effective for MDD (George, 2010; Lefaucheur et al., 2014; Leggett et al., 2015; Milev et al., 2016; McClintock et al., 2017). Prior studies (case series and reports) of rTMS in MDD patients below the age of 22 are limited but encouraging, but substantial knowledge gaps remain (Donaldson et al., 2014).

OBJECTIVE

With this in mind, we conducted a trial of LDLPFC rTMS in youth with treatment resistant MDD. We hypothesized that rTMS would reduce depressive symptom severity in youth with MDD.

DESIGN

Open label trial of TMS.

METHODS

This study was approved by the Conjoint Health Research Ethics Board (CHREB) for the University of Calgary.

Participants

Participants were recruited from the community and clinics in our area. Inclusion criteria were: (1) age 12-22 years, (2) diagnosis of MDD, based on an interview with the Kiddie Schedule for Affective Disorders and Schizophrenia Present and Lifetime version (K-SADS-PL)(Kaufman et al., 1997) with a symptom severity of 40 or greater on the Children's Depression Rating Scale Revised (CDRS-R)(Poznanski et al., 1985), (3) history of failing to respond to at least one selective serotonin reuptake inhibitors (SSRI) trial (minimum 8-week treatment at an adequate dose; retrospectively determined on interview), and (4) ability to provide informed consent. Psychotropic medications were allowed if the dose has been stable for six weeks with adequate compliance, and with a commitment to not change

medication/dosage during the trial period, unless deemed medically necessary. Exclusion criteria included: (1) previous seizures or epilepsy, (2) hypertension, (3) previous neurological or psychiatric diagnoses (specifically - bipolar disorder or psychosis) (4) pregnancy, (5) implanted metal or medical device, or (6) left-handedness.

Assessments

Participants were assessed at baseline, weekly during rTMS, and at the completion of treatment. Core clinical assessments were designed to confirm diagnosis (baseline), define symptoms, and assess treatment response. The K-SADS-PL (Kaufman et al., 1997), was used to assess both present and lifetime psychiatric symptomatology. The CDRS-R (Poznanski et al., 1985) was administered at baseline and treatment completion to quantify moderate to severe depressive symptom severity in participants. The Hamilton Depression Rating Scale (Ham-D)(Hamilton, 1967) and Beck Depression Inventory (BDI)(Beck et al., 1997), were used to assess depressive symptoms at baseline, the end of each week for safety monitoring, and after treatment completion. The Hamilton Anxiety Rating Scale (Ham-A)(Hamilton, 1959), to assess anxiety levels, was also administered at baseline and after treatment completion. We endeavored to complete assessments within two weeks of initiation and termination of rTMS.

The primary outcome measure of treatment response was defined as a greater than 50% reduction in Ham-D scores from baseline to end-point. A secondary exploratory measure of clinically meaningful response was also preset at 30% based on American College of Neuropsychopharmacology (ACNP) recommendations (Rush et al., 2006). We also examined predefined criteria for remission (Ham-D score ≤ 7 post-rTMS) and partial remission (Ham-D score ≤ 10 post-rTMS and a $\geq 50\%$ reduction in Ham-D score).

rTMS

TMS was performed at the Alberta Children's Hospital. The TMS intervention utilized a Magstim SuperRapid₂, air-cooled 90mm figure-of-8-coil (Magstim, Wales UK). Using a neuronavigation system (Brainsight2, Rogue Research, Montreal), the TMS coil was monitored in real time and co-registered with the individual's structural MRI. Imaging was performed on a 3T GE MR750w scanner using a 24-channel head coil. Anatomical scan parameters were: Axial T1-w 3D BRAVO with TR = 8204 milliseconds, TE = 3.168 milliseconds, flip angle = 10 degrees, 226 slices with 0.8 mm thickness, 300 x 300 matrix.

On the first day, motor evoked potentials (MEP) were recorded to determine the resting motor threshold (RMT) in the standard manner (Kirton et al., 2010). To initially locate the DLPFC target site, the 5-cm rule was applied, in which the scalp position 5cm anterior to the hotspot along a line to the nasion was marked (George et al., 1995; George et al., 1996; Herwig et al., 2001; Herwig et al., 2003). Neuronavigation confirmed accurate DLPFC (adjusted if needed) targeting. The TMS coil was subsequently placed tangential to the scalp, and angled at 45 degrees to the midline and fixed over the target using a mechanical arm. The target was marked on the neuronavigation system, allowing real time targeting and accurate session to session reliability.

rTMS was applied at 10 Hz. Each train consisted of 40 suprathreshold (120% RMT) pulses over 4 seconds with an inter-train interval of 26 seconds. Treatment sessions lasted 37.5 minutes (75 trains/3000 pulses), and occurred at the same time of day on every weekday for a period of three weeks (15 days total). During TMS, only passive activities were allowed (i.e., watching movies or TV, listening to music). Three weeks of treatment was selected based on existing rTMS evidence in adult MDD and our rTMS experience in pediatric stroke (Kirton et al., 2008; Davis, 2014). Participants were monitored for adverse events and tolerability using a Pediatric TMS Safety and Tolerability Measure (Garvey, 2005) on days 1, 6, and 11. Items were self-rated.

STATISTICAL CONSIDERATIONS

For the primary outcome, we hypothesized that rTMS would result in a significant reduction in depression symptom severity as measured by the Ham-D. We used a paired t-test comparing baseline to post-rTMS with $p < 0.005$. We increased the threshold in keeping with recommendations designed to improve reproducibility (Benjamin et al., 2017). For exploratory measures (i.e., CDRS, BDI, Ham-A) we used a paired t-test comparing baseline to post-rTMS with $p < 0.01$ to correct for multiple comparisons (Bonferroni). Analyses were performed with IBM SPSS (version 24; New York, USA).

REFERENCES

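### Remission is a post-treatment Ham-D of 7 or less with no Ham-D minimum at entry, so it can be counted without improvement and does not nest with partial remission

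*Combined protocol and SAP*

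**What the plan says.** All of this is in the combined protocol and SAP.

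- **Entry (METHODS, Participants).** Participants need a K-SADS-PL diagnosis of MDD "with a symptom severity of 40 or greater on the Children's Depression Rating Scale Revised (CDRS-R"). None of the four inclusion or six exclusion criteria mentions the Ham-D.
- **Ham-D schedule (METHODS, Assessments).** The Ham-D and BDI "were used to assess depressive symptoms at baseline, the end of each week for safety monitoring, and after treatment completion".
- **Primary response (Assessments).** This is "defined as a greater than 50% reduction in Ham-D scores from baseline to end-point".
- **Exploratory response (Assessments).** "A secondary exploratory measure of clinically meaningful response was also preset at 30" per cent.
- **Remission (Assessments).** The plan examines "predefined criteria for remission (Ham-D score ≤ 7 post-rTMS"). No baseline or change condition is attached.
- **Partial remission (same sentence).** This is "partial remission (Ham-D score ≤ 10 post-rTMS and a" reduction of 50% or more.
- **Test (STATISTICAL CONSIDERATIONS).** "We used a paired t-test comparing baseline to post-rTMS with" a threshold of 0.005. That section does not mention remission and limits no outcome to a subset by baseline Ham-D.

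**The concern.** Severity is guaranteed on one scale and remission is read on another. An end-state cut-off describes recovery when everyone starts above it. Here nothing in the plan ensures that on the Ham-D, so a participant can enter the trial already meeting the remission criterion and be counted as remitted whatever happens during treatment.

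The categories are also out of order. The lesser outcome, partial remission, demands a 50% fall, and the greater outcome, full remission, demands none. A full remission therefore need not be a partial remission, and the two proportions cannot be read on one scale.

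What is at stake is the meaning of the remission proportion. The design is an open-label trial with no control arm described, so remissions that need little or no change cannot be netted out against a comparison group.

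**Working it through.** The plan states no sample size, expected remission rate or Ham-D distribution, so it has no figure of its own to reproduce. The check has an exact part and an assumed part.

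**1. What the rules allow (exact, whole-number scores).** For baseline b, the smallest improvement that still counts as remission is a final score of 7. The percentage fall is then 100 × (b − 7)/b. The 30% criterion is taken as a fall of at least 30% on the Ham-D.

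| Baseline to final | Fall | Remission | Partial remission (≤10 and ≥50%) | Response (>50%) | 30% criterion |
|---|---|---|---|---|---|
| 5 to 7 | −40.0% (worse) | yes | no | no | no |
| 7 to 7 | 0% | yes | no | no | no |
| 8 to 7 | 12.5% | yes | no | no | no |
| 10 to 7 | 30.0% | yes | no | no | yes |
| 12 to 7 | 41.7% | yes | no | no | yes |
| 13 to 7 | 46.2% | yes | no | no | yes |
| 14 to 7 | 50.0% | yes | yes | no | yes |
| 15 to 7 | 53.3% | yes | yes | yes | yes |

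So remission is possible with no fall at any baseline of 7 or less, and with a fall below 50% at any baseline of 13 or less.

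**2. How often this might happen (assumed).** The assumptions are a normal baseline with mean m of 15, 18 or 20 and SD 5, and a post score of (m − mean fall) + 0.6 × (baseline − m) plus normal error with SD 4. The mean fall is 4 or 8 points. Scores are rounded to whole numbers, and 2,000,000 pairs are simulated per scenario.

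The share starting at 7 or less is Φ((7.5 − m)/5):
- m = 15: Φ(−1.5) = 6.7%
- m = 18: Φ(−2.1) = 1.8%
- m = 20: Φ(−2.5) = 0.6%

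| Mean fall | Quantity | m = 15 | m = 18 | m = 20 |
|---|---|---|---|---|
| 4 | Remission with no fall, of all participants | 1.7% | 0.4% | 0.1% |
| 4 | Counted remissions lacking a ≥50% fall | 32% | 28% | 24% |
| 8 | Remission with no fall, of all participants | 1.0% | 0.3% | 0.1% |
| 8 | Counted remissions lacking a ≥50% fall | 12% | 10% | 9% |

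The two quantities have different denominators. The second is a share of remissions, and it includes people with real falls of 30% to just under 50%.

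**3. Effect of limiting the count to baseline above 7.** In the scenario with the largest effect (m = 15, mean fall 4), 24.1% of participants are remissions, and 4.7% of participants are remissions that started at 7 or less. With 6.6% of simulated participants starting there, the restricted rate is (24.1 − 4.7)/(100 − 6.6) = 19.4/93.4 = 20.8%. Adding the 50% fall without restricting the denominator gives about 16% in the same scenario.

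**The case against.** An absolute cut-off is a coherent definition of remission. Remission describes where a person ends and response describes how far they moved, and the plan defines the two separately. On that view 12 to 7 is no contradiction: it is an end state reached by a fall that also passes the plan's own 30% criterion. Entry requires an interview diagnosis of MDD, a CDRS-R of at least 40 and a failed SSRI trial, so a baseline Ham-D of 7 or less should be uncommon. Remission is an additional outcome with no test attached, and rewriting its definition would alter a predefined criterion.

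Most of this stands. It is a good reason to keep the cut-off, and it limits the weight of the point. It does not answer two things. The end-state argument presupposes that people begin outside the end state, which the entry criteria make likely but do not ensure on this scale. And the plan attaches a change condition to partial remission but not to full remission, so its own two categories do not follow one principle.

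A reader might infer more than this:

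- **That remissions without improvement are common.** The documents give no baseline scores. Under the assumptions above, such cases are at most 1.7% of participants.
- **That the main efficacy result is affected.** It is not. The paired t-test and the >50% response both compare each participant with their own baseline.
- **That one or two such participants would visibly move the rate, or that the rate will be set against adult rTMS results.** The plan states no sample size and plans no such comparison.

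**Conclusion.** The point holds as a gap in the counting rule for remission, and as a failure of full and partial remission to nest. Both follow from the text and whole-number arithmetic, without assumptions.

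The size does rest on assumptions, because no Ham-D distribution is given. With baseline mean 15 to 20, SD 5, slope 0.6, residual SD 4 and a mean fall of 4 or 8, about 0.6% to 7% of participants start at 7 or less, 0.1% to 1.7% of all participants are remissions with no fall, and 9% to 32% of counted remissions lack a 50% or greater fall. The no-change and worsening cases are the clear miscount but should be rare. Baselines of 8 to 13, where the fall is real but may be modest, are the more plausible source of remissions that would not qualify as partial remissions. The documents show what the rule permits, not that it occurred, and they do not support calling the cut-off itself wrong.

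**What to change.** Add a short statement to the statistical section:

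- Keep every participant in the paired t-test.
- Keep the predefined cut-off of 7, but count remission only among participants whose baseline Ham-D is above 7. Report how many started at 7 or less.
- Beside it, as a sensitivity result, give the number who reached 7 or less with a fall of 50% or more, so that full and partial remission can be read on the same basis.

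Baseline and post-treatment Ham-D scores are already collected, so this costs a recount and no new data. The downside is a slightly lower remission rate and a slightly smaller denominator. In the scenario with the largest effect, the rate goes from 24.1% to 20.8% and the denominator loses just under 7% of participants. The sensitivity count is stricter and leaves out real improvements such as 13 to 7, which is why it belongs beside the predefined criterion and should not replace it.

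### Do the Ham-D response, remission and partial-remission rules conflict in a way that requires a change to the plan?

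*Combined protocol and SAP*

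**What the plan says.** All the category rules are in METHODS, Assessments. The primary outcome measure of "treatment response was defined as a greater than 50% reduction in Ham-D scores from baseline to end-point". Next comes a lower exploratory threshold: "A secondary exploratory measure of clinically meaningful response was also preset at 30" per cent. The paragraph closes with a sentence that begins "We also examined predefined criteria for remission" and sets the criteria for "remission (Ham-D score ≤ 7 post-rTMS) and partial remission (Ham-D score ≤ 10 post-rTMS and a" reduction of at least 50%. Remission is a post-treatment Ham-D of 7 or less, with no condition on percentage change. Partial remission is a post-treatment Ham-D of 10 or less together with a reduction of at least 50%, with no lower limit on the score.

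Two other places bear on the point. Under Participants, entry severity is set on a different scale, "with a symptom severity of 40 or greater on the" CDRS-R, so no minimum baseline Ham-D is stated. Under STATISTICAL CONSIDERATIONS, the primary hypothesis concerns Ham-D severity: "We used a paired t-test comparing baseline to post-rTMS with" a threshold of p < 0.005. That section attaches no test, threshold or presentation rule to response, remission or partial remission.

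**The concern.** Two features look like defects when the definitions are read together.

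The first is the inequality sign. Response needs a fall of more than 50%, and partial remission needs one of at least 50%. Ham-D takes whole-number values, so exact halving can happen. A participant could then appear as a partial remitter and, on the named primary outcome measure, as a non-responder, with nothing in the plan to explain it.

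The second is the overlap. Remission and partial remission are listed side by side, which can suggest separate groups. As written, most remitters are also partial remitters. A reader who added the two rates would count those participants twice and overstate the benefit. In an open-label trial without a comparison group, such rates are likely to be quoted, so a misreading would matter to how the results are received.

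**Working it through.** The plan states no expected rate, sample size or Ham-D distribution for these categories, so there is no figure to reproduce. The definitions can be checked exactly.

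**Inputs** (all from Assessments), with whole-number baseline b and post-treatment score p:
- response: 2(b − p) > b
- remission: p ≤ 7
- partial remission: p ≤ 10 and 2(b − p) ≥ b

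**Sign mismatch.** Partial remission without response requires 2(b − p) ≥ b but not 2(b − p) > b. That leaves 2(b − p) = b, so b = 2p, with p ≤ 10. Ten pairs qualify: 2→1, 4→2, 6→3, 8→4, 10→5, 12→6, 14→7, 16→8, 18→9 and 20→10. Seven of them have a baseline of 8 or more. No other pair shows this conflict.

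**Overlap.** If b ≥ 14 and p ≤ 7, then (b − p)/b ≥ (14 − 7)/14 = 50%, so every such remitter is also a partial remitter. The bound is sharp: 13→7 is a fall of 6/13 = 46.2%, which is remission but not partial remission. The categories are therefore nested only from baseline 14 upward.

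**Remission without response.** Over baselines 8 to 30 there are 16 such pairs. Twelve are falls of less than half from a baseline of 13 or lower (for example 12→7 and 13→7). Four are exact halvings (8→4, 10→5, 12→6 and 14→7). So most of the disagreement between remission and response comes from using an absolute cut-off beside a relative one. Aligning the two 50% signs would not remove those twelve.

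**Size under assumptions.** Take baseline as a rounded normal with mean 16 to 24 and SD 4, and mean change −5 to −10 with SD 6, both held to 0–52. None of these values is in the documents.
- Partial remission without response: 0.57% to 2.87% of participants. With an assumed n of 30, the expected count is 30 × 0.0057 = 0.2 to 30 × 0.0287 = 0.9.
- Share of partial remitters who are full remitters: 51% to 89%.
- Sum of the two rates divided by the proportion meeting either: 1.5 to 1.9.
- Example (baseline mean 20, change −5): remission 14.9%, partial remission 21.0%, either 21.5%. Adding the two gives 35.9%, and 35.9/21.5 = 1.67.

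With baseline SD 3 to 5 (means 16, 20 and 24) and change SD 4 to 8, the ranges widen to 0.3% to 4.5%, 28% to 92%, and 1.3 to 1.9.

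**What uses these categories.** The paired t-test takes the Ham-D scores themselves. Neither the sign nor the overlap enters it.

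**The case for a change.** The strongest case for acting is that the cost is trivial. One sentence in a results table would prevent a reader from turning roughly 21% into an apparent 36%, as in the example above, and a footnote would explain a participant who is a partial remitter but not a responder. The plan settles neither point, and response is named as the primary outcome measure.

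The facts behind this stand, but they do not show that a planned rule is wrong. The 1.5 to 1.9 factor measures the error of someone who adds two rates that the plan never adds and never calls exclusive. A limit of 10 or less visibly contains a limit of 7 or less, and the plan's other graded pair, response at 50% and clinically meaningful response at 30%, is also cumulative. Partial remission is nowhere said to be a subset of response, so the two signs belong to two separate definitions.

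The obvious remedies also carry faults. A label such as *at least partial remission* implies that all remitters are included, which 13→7 contradicts. Changing the partial-remission rule to more than 50% would alter a predefined criterion and make 14→7 a remission without partial remission.

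**Conclusion.** The concern is correct as a description but calls for no change. The definitions overlap, and they disagree at one boundary, yet each can be applied without ambiguity and gives a definite rate. The sign mismatch is confined to exact halvings to 10 or below. The overlap is a legitimate cumulative reading that the plan leaves unstated, and an analyst tabulating the results can note it there without touching a cut-off. No reported rate, test or conclusion depends on it, and the primary paired t-test at p < 0.005 is unaffected.

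That the t-test is unaffected, and where the boundary cases lie, follows from the definitions alone and assumes only whole-number scores. How many participants are affected cannot be determined from the documents, because the percentages given rest entirely on assumed Ham-D means and SDs and the counts on an assumed n of 30.

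### The only stated adverse-event and tolerability form is self-rated on days 1, 6 and 11, so none is stated after sessions 12-15, after the course, or at early stopping

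*Combined protocol and SAP*

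**What the plan says.** The rTMS section of the Methods names one instrument for harms: "Participants were monitored for adverse events and tolerability using a Pediatric TMS Safety and Tolerability Measure". It was given "on days 1, 6, and 11. Items were self-rated". The same section says that sessions "occurred at the same time of day on every weekday for a period of three weeks (15 days total").

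The Assessments section gives the general schedule: "Participants were assessed at baseline, weekly during rTMS, and at the completion of treatment". It says of the Ham-D and BDI that they "were used to assess depressive symptoms at baseline, the end of each week for safety monitoring, and after treatment completion". The CDRS-R and Ham-A are also due at completion.

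The document describes no other adverse-event recording. It mentions no log of spontaneous reports, no check at each session, no end-of-course tolerability form and no form at withdrawal. It does not state the form's recall period, or whether the form is completed before or after that day's stimulation.

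**The concern.** The sentence on monitoring covers adverse events and tolerability together, and it assigns both to one form on three days. If those are treatment days, each form falls on the first session of a treatment week. None falls at the end of a week, or at the end of the course when cumulative exposure is greatest. Because the form is tied to fixed days, a participant who stops between forms, possibly because stimulation was hard to tolerate, gives no rating at that point.

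This bears on what the trial can report. The Introduction regards rTMS as well established in adults, but describes the evidence below age 22 as sparse though promising, with important gaps. The Design section describes an open-label trial, and no control group is mentioned. Any statement about tolerability would therefore be descriptive and would rest on these forms alone. Effects that accumulate over sessions, or that lead to stopping, are the ones this schedule is least likely to record.

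**Working it through.** **Inputs.** All come from the Methods.

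- Course: every weekday for three weeks, 15 days in total (rTMS section).
- Session: "Treatment sessions lasted 37.5 minutes (75 trains/3000 pulses"), built from trains of 40 "pulses over 4 seconds with an inter-train interval of 26 seconds" (rTMS section).
- Tolerability form: days 1, 6 and 11 (rTMS section).
- Ham-D and BDI: baseline, end of each week, and after completion (Assessments section).

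**Step 1. Reproduce the plan's own figures.**

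- Sessions: 5 weekdays × 3 weeks = 15, as stated.
- Pulses per session: 75 trains × 40 = 3000, as stated.
- Session length: 75 × (4 + 26) s = 2250 s = 37.5 min, as stated.
- Whole course: 15 × 3000 = 45,000 pulses.

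**Step 2. What does day 11 mean?** Read as treatment days, days 1, 6 and 11 are the first sessions of weeks 1, 2 and 3. Read as calendar days, at least one of days 6 and 11 falls on a weekend for every start weekday except Friday, and 6 to 8 sessions would follow day 11. The treatment-day reading fits a weekday schedule better, gives the smaller gap, and is used below.

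**Step 3. Exposure after the last form.**

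- Form completed after session 11: 15 − 11 = 4 sessions; 4/15 = 26.7%; 4 × 3000 = 12,000 of 45,000 pulses.
- Form completed before session 11: 15 − 10 = 5 sessions; 5/15 = 33.3%; 5 × 3000 = 15,000 of 45,000 pulses.

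**Step 4. Share of events the forms could capture.** Assume that events are spread evenly over the 15 sessions and that each form is completed after its session. Compare the current schedule with one that adds a form at session 15.

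| Assumed recall period | Days 1, 6, 11 | Days 1, 6, 11, 15 |
|---|---|---|
| Everything since the previous form | 11/15 = 73% | 15/15 = 100% |
| Current session only | 3/15 = 20% | 4/15 = 27% |

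**Step 5. Early stopping.** A participant who stops after session 10 last completed the form on day 6, so sessions 7-10 (10 − 6 = 4 sessions) go unrated under either recall period. The same holds for sessions 2-5 if stopping comes after session 5.

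**Step 6. What follows day 11.** The week-3 Ham-D and BDI fall at about session 15, and both are repeated after completion. The Assessments section gives them a safety purpose, but describes their content as depressive symptoms.

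**The case against.** The strongest objection is that safety is monitored to the end. The Ham-D and BDI are given at "the end of each week for safety monitoring, and after treatment completion". A reader might infer from the three-day form schedule that no safety rating of any kind follows the last four sessions or the completed course. The documents do not support that: two scales the plan itself labels as safety monitoring come after both. This part of the objection stands and limits the point to adverse events and tolerability of stimulation. It does not close that gap, because nothing presents these scales as recording stimulation effects.

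Second, the plan promises no tolerability conclusion. The Objective, the outcome definitions and the Statistical Considerations all concern efficacy measures. That is correct, so the point limits what could be reported and does not contradict a stated aim. The form is nevertheless collected for a purpose, and its coverage decides what can be said from it.

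Third, a reader might take the Introduction's mention of safety concerns in youth to be about rTMS. It is about existing treatment options for depression. The relevant support is the separate remark on gaps in rTMS evidence below age 22.

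Fourth, the capture rates rest on an unstated recall period and on evenly spread events. Under current-session recall the added form gains only one session in 15. This also stands. The figures are a range under assumptions, and nobody can say from the documents that events were in fact under-counted.

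Fifth, one form per treatment week is a regular schedule, and the text is in the past tense, so forms may no longer be addable. Regularity does not help with the end of the course or with early stopping. The question of timing decides which remedy applies.

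**Conclusion.** The point holds for adverse events and tolerability specifically. As written, the plan states no such form after sessions 12-15, after the course, or at early stopping. The uncovered part of the course is 4 of 15 sessions (12,000 of 45,000 pulses) on the treatment-day reading with the form completed after session 11. It is 5 of 15 if the form comes before that session. The count rests on the stated schedule and is firm, whereas the share of events missed is not known. The improvement from a last-session form runs from one extra session in 15 to full coverage, depending on recall.

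The documents do not show that safety monitoring stops at day 11, or that any event was missed. Adverse events may have been recorded in ways the text does not describe. The primary efficacy analysis is unaffected. This is a modest gap that is cheap to close.

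**What to change.** If data can still be collected, give the same self-rated form at the last session (day 15), after stimulation, alongside the week-3 Ham-D and BDI. Give it also at withdrawal to anyone who stops early. State the form's recall period and whether it is completed before or after the session. The cost is one short form per participant at a visit already attended, a few minutes of participant time, and a line or two in the protocol.

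If collection is finished, limit any tolerability statement to the sessions covered by the forms, up to day 11, and say so. Describe any other adverse-event recording that took place; if it covered the whole course, a sentence saying so would largely answer the point. No change to treatment is proposed.

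### As written, the primary Ham-D test uses only participants with both scores: no analysis set or missing-score rule is stated, and the weekly ratings enter no efficacy analysis

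*Combined protocol and SAP*

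**What the plan says.** STATISTICAL CONSIDERATIONS gives one primary analysis, on the Ham-D: "We used a paired t-test comparing baseline to post-rTMS with" p < 0.005. The exploratory scales (CDRS, BDI, Ham-A) use the same two time points.

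METHODS, Assessments, sets the schedule: "Participants were assessed at baseline, weekly during rTMS, and at the completion of treatment". Of the Ham-D and BDI it says that they "were used to assess depressive symptoms at baseline, the end of each week for safety monitoring, and after treatment completion". On timing it says: "We endeavored to complete assessments within two weeks of initiation and termination of rTMS". Response is a "greater than 50% reduction in Ham-D scores from baseline to end-point"; remission and partial remission use the post-rTMS Ham-D score.

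No section names an analysis set, a minimum number of sessions, a rule for a missing score, an imputation method or a sensitivity analysis. The end-point is not defined. The text does not say whether the rating after completion is the same as the end-of-week-3 rating, or how a participant who stops early is rated and counted. DESIGN reads "Open label trial of TMS", and no comparison group is described.

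**The concern.** A paired t-test needs both members of each pair. Without a missing-score rule, anyone who lacks the baseline or post-rTMS Ham-D leaves the primary analysis. Treatment takes 15 weekday visits over three weeks, so some early exits are plausible.

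With no comparison group described, there is no second arm in which a similar loss might partly cancel. If the people without a final score changed more or less than the others, the difference goes straight into the mean change and the response rate. The plan already collects Ham-D every week. Those ratings carry information about people who leave, and the analysis does not use it.

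**Working it through.** **Inputs.** The documents give no sample size, SD, effect size or dropout rate, so there is no stated figure to reproduce. All numerical inputs below are assumed.

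**Step 1: how loss enters the mean.** With a proportion d missing,

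mean of all treated = (1 - d) × completer mean + d × dropout mean,

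so completer mean - mean of all treated = d × (completer mean - dropout mean).

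Example: completers change by -10, dropouts by -5, d = 0.20. All treated: 0.80 × (-10) + 0.20 × (-5) = -9.0. Complete pairs report -10, a difference of 0.20 × (-5) = -1.0. If the two groups change equally, or d = 0, the difference is zero.

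**Step 2: size under assumed inputs.** Simulation with 1,000,000 subjects per correlation value. Mean changes are -2, -4, -6 at weeks 1 to 3; SDs of change are 3.5, 5, 6; serial correlation (AR(1)) is 0.5, 0.7 or 0.85. Loss of the final score follows a logistic model with odds ratio 2 or 3 per SD of change. The rows below have poorer responders leaving.

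| Loss depends on | Missing | Error of complete pairs (points) | Share left by a likelihood model, weeks 1-2 seen | Share left, week 2 also missing |
|---|---|---|---|---|
| week-2 score | 10% | 0.20-0.50 | about none (within 0.01 points) | about 29-77% |
| week-2 score | 20% | 0.39-0.95 | about none (within 0.01 points) | about 29-77% |
| unseen final score | 10% | 0.40-0.59 | 28-78% | 49-94% |
| unseen final score | 20% | 0.77-1.11 | 28-78% | 49-94% |

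In these rows improvement is overstated. If better responders leave, the sign reverses. With loss driven by week 2, improvement is then understated by about 0.20-0.51 points at 10% missing and 0.39-0.96 at 20%. I reran these cases in both directions and obtained the same figures within simulation error.

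**Step 3: comparison with sampling error.** Standard error = 6 / √(n(1 - d)). For n = 20, d = 0.20: 6/√16 = 1.50. For n = 30, d = 0.10: 6/√27 = 1.15. For n = 30, d = 0.20: 6/√24 = 1.22. The largest week-2-driven error at 20% missing (about 0.95) is below 1.22, and at 10% missing (about 0.5) it is below 1.15.

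**Step 4: response rate.** With an assumed baseline of 20, response means a fall of more than 10. The true rate is Φ((-10 + 6)/6) = Φ(-0.667) = 25.2%. Ratios to the true rate, loss driven by week 2:

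| Who leaves | Missing | Completers' rate | Missing counted as non-response |
|---|---|---|---|
| poorer responders | 10% | 1.04-1.08 | 0.93-0.97 |
| poorer responders | 20% | 1.08-1.17 | 0.86-0.93 |
| better responders | 10% | 0.88-0.95 | 0.79-0.86 |
| better responders | 20% | 0.77-0.91 | 0.62-0.73 |

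Imputing the missing final score from weeks 1 and 2 gives 1.00 times the true rate in both directions, provided those weeks are seen and the normal model is right.

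**Step 5: agreement with the planned test.** On simulated complete data with n = 20 and an unstructured covariance, the final contrast has t = -5.802 with four time points, the same as the paired t. With five time points and completion as the end-point, both are -5.067. Making a separate week-3 rating the end-point gives -4.453, which is a different test from the planned one.

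**The case against.** The strongest reply is that the problem may not exist. No dropout is reported, and with full follow-up the planned test is sound. That stands, and it limits the point to unknown size.

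Second, a reader might infer that the plan overstates benefit because poorer responders drop out. The documents do not support that direction: improved participants may also miss the final visit, and the error then has the opposite sign.

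Third, the error is small against noise. At an assumed n of 20 to 30 it lies below one standard error. Adding 0.2 to 0.95 points to a true null would raise the rejection rate at 0.005 only to about 0.005-0.021. So there is no ground for inferring that the primary conclusion would change. What remains is that at 20% missing, in the week-2-driven small-sample runs, the model's root mean square error was lower than that of complete pairs in every scenario: 1.13-1.53 with weeks 1-2 seen and 1.16-1.57 with week 1 only, against 1.29-1.72.

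Fourth, the text is in the past tense ("we conducted a trial of LDLPFC rTMS in youth with treatment resistant MDD") and cites 2017 sources. If the data had been seen, a new primary model cannot be prespecified. This stands and limits the status of the fix.

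Fifth, the word end-point could mean the last available score. No such rule is stated, however, and the primary test refers to the post-rTMS score.

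**Conclusion.** The point holds as a gap that is cheap to close. As written, the primary analysis is a complete-pairs analysis, with no analysis set or missing-score rule and no efficacy use of the weekly Ham-D. Neither the size nor the direction of any bias can be determined from the documents. It is nil if no scores are missing or if missingness is unrelated to outcome.

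The illustrated error, roughly 0.2 to 0.95 points on a 6-point fall at 10-20% missing, rests entirely on the assumed means, SDs, correlations and week-2-driven dropout. A model on the weekly scores removes it in that case, but only partly when week 2 is also missing or when loss depends on the unseen final score.

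A reader might also infer that the completers' rate and the missing-as-non-response rate bracket the true response rate. They do so only if people with missing scores respond no more often than completers; when better responders leave, both rates fall below the truth.

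**What to change.** - **Mean change.** Include everyone who received at least one session in a repeated-measures mixed model on baseline and all Ham-D ratings, with time as a factor, small-sample degrees of freedom, and unstructured covariance with a pre-stated simpler fallback. Test the end-point contrast at 0.005.
- **End-point.** State whether the end-of-week-3 and completion ratings are one visit and which is the end-point. One visit means four time points and 4 × 5/2 = 10 covariance parameters; two visits mean five and 5 × 6/2 = 15. Naming completion keeps the planned test when data are complete. State how a score taken when someone stops early is used.
- **Response and remission.** Multiply impute missing end-point scores from baseline and the weekly ratings under the same model. Show the completers' rate and the missing-as-non-response rate as sensitivity analyses, without calling them bounds.
- **Not-at-random sensitivity.** Apply a delta adjustment to the mean change in both directions, for example up to 6 points worse and up to 6 better than predicted. The resulting shift is d × delta: 0.10 × 6 = 0.6 or 0.20 × 6 = 1.2 points.
- **Reporting.** Give the numbers treated, analysed and missing.
- **Status.** If the data had already been seen, keep the planned t-test as primary and label all of this post hoc and supportive.

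The cost is wording and slightly more analysis, with no new visits or data. Response rates may look less favourable, a very small sample may force the simpler covariance, and the model helps little for early exits with few weekly scores. The lack of a comparison group is not addressed.
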